4.4 Blinding

This section is not applicable as this is an open-label study.

4.5 Assignment and Allocation

Subjects will be enrolled through Interactive Response Technology (IRT). The site personnel will dispense the treatment according to the IRT system's assignment. Specific procedures for enrollment through the IRT are contained in the study procedures manual.

5 TREATMENTS AND EVALUATION

5.1 Dosing and Administration of Study Drug(s) and Other Medication(s)

5.1.1 Dose/Dose Regimen and Administration Period

Aseptic technique must be used for the preparation and administration of ASP1650. Detailed instructions for the administration of ASP1650 will be provided in the Pharmacy Manual.

ASP1650 will be administered intravenously on day 1 of each cycle (each cycle has 14 days). All subjects will be treated for a maximum of 12 cycles or until the subject meets study treatment discontinuation criteria.

The 1000 mg/m² Q2W dose is administered as a 2-hour infusion and the 1250 mg/m² Q2W and 1500 mg/m² Q2W doses are administered as a 3-hour infusion, any of which may be interrupted or slowed down to manage toxicity.

The infusion of ASP1650 should be completed in less than 6 hours from the start of infusion.

5.1.2 Increase or Reduction in Dose of the Study Drug(s)

5.1.2.1 ASP1650 Increase or Reduction

Following the safety lead-in, subjects will be treated with the RP2D of ASP1650. Subjects enrolled in the 1000 mg/m² Q2W dose level in the Safety Lead-in phase will be dose escalated to 1500 mg/m² after the RP2D has been deemed tolerable. Dose increase above the RP2D is not allowed. If the tolerable RP2D is established as 1500 mg/m² Q2W, then dose

reduction to 1250 mg/m² Q2W is allowed due to AEs, per investigator discretion. Further dose reduction to 1000 mg/m² Q2W is allowed due to AEs, per investigator discretion, however, dose reduction below 1000 mg/m² Q2W is not allowed. Dose re-escalation is allowed up to the RP2D based on investigator discretion. Body surface area should only be recalculated if there is a weight change of at least 10% since the last body surface area calculation.

5.1.2.2 ASP1650 Interruption or Permanent Discontinuation

There is a +5 day allowable window for dosing ASP1650 (with the exception of C1D1). If ASP1650 treatment is delayed more than 2 days then it should be administered as soon as the reason for delay has resolved, which will then become day 1 of the next cycle. Permanently discontinue ASP1650 treatment if delayed beyond 28 days from when the next study treatment was scheduled to be administered. However, restarting study treatment after dosing delay (beyond ≥ 28 days from when the next study treatment was scheduled to be administered) may be allowed based on investigator consultation with, and approval of, the Astellas medical monitor.

5.1.2.3 Guidelines for Infusion-Related Reactions for ASP1650

Subjects should be closely monitored for IRRs during infusion and post-infusion to facilitate early identification and management. The management of such toxicities should be based on investigator utilizing institutional standard of care, published guidelines and the general guidelines provided in [Table 3](#) below.

A subject with an infusion reaction should be evaluated specifically for the symptoms and signs that are highly suggestive of anaphylaxis (urticaria, repetitive cough, wheeze and throat tightness/change in voice). A careful examination of the skin is advised in order to detect urticaria, which often appears first in the neck, trunk, abdomen and axillae.

Not all anaphylactic reactions manifest as anaphylactic shock. Because anaphylaxis can recur and worsen with re-exposure, permanently discontinue ASP1650 for any subject having a reaction with features (even if mild) that are highly suggestive of anaphylaxis.

Table 3 Infusion-Related Reactions

Infusion-Related Reactions	
CTCAE Grade	Management
Grade 1 standard infusion reaction	Continue infusion and closely monitor the subject. For the next infusion: 
 • Pre-medicate as appropriate.* • Closely monitor the subject for symptoms and signs of an infusion reaction.
Grade 2 standard infusion reaction	Interrupt. Medical management as per type of reaction. Resume infusion once toxicity Grade \leq 1 and reduce the infusion rate for the remaining infusion. For the next infusion: 
 • Increase total infusion time (reduce infusion rate). • Pre-medicate as appropriate.* • Closely monitor the subject for symptoms and signs of an infusion reaction.
Grade 3 or 4 standard infusion reactions or any reaction with features of anaphylaxis	Stop the infusion immediately. Institute appropriate medical management immediately based on the type of reaction. Permanently discontinue ASP1650 Once the subject has been stabilized, collect blood for a cytokine/chemokine panel. If the reaction is suggestive of anaphylaxis, collect blood for serum total tryptase level (levels typically peak within 3 hours after the onset of symptoms).

CTCAE: Common Toxicity Criteria for Adverse Events

* At the investigators discretion, anti-histamines may be used as pre-medication for the next infusion. Systemic corticosteroids should be avoided or minimized while subject is on study treatment unless required for management of an emergent medical condition (e.g., severe hypersensitivity reaction).

5.1.3 Previous and Concomitant Treatment (Medication and Non-Medication Therapy)

Previous treatment is defined as medication and non-medication therapy (e.g., diet, sodium intake restriction, rehabilitation, etc.) undergone before entering the investigational period.

Prohibited Prior Treatment or Therapies

- Systemic immunosuppressive therapy, including systemic corticosteroids within 14 days prior to first dose of study treatment. Subject using a physiologic replacement dose of hydrocortisone or its equivalent (defined as up to 30 mg per day of hydrocortisone or up to 10 mg per day of prednisone) or a single dose of systemic corticosteroids is eligible. Subject who received systemic steroids for asymptomatic CNS metastases within 14 days prior to first dose of study treatment is eligible.
- Other investigational agents or devices within 28 days prior to first dose of study treatment.

- Prior anti-cancer mAb within 4 weeks prior to study day 1 or ongoing toxicity (i.e., > grade 1 or at baseline) from AE due to mAb agents administered more than 4 weeks earlier.
- Prior chemotherapy, targeted small molecule therapy, or radiation therapy within 2 weeks prior to study day 1 or ongoing toxicity (i.e., > grade 2 or at baseline) from AEs due to a previously administered agent

Concomitant treatment means medication and non-medication therapy (e.g., opioids, sodium intake restriction, rehabilitation, etc.) used during the investigational period.

All concomitant treatments will be recorded in the eCRF.

Prohibited Concomitant Treatment

The following are strictly prohibited:

- Systemic immunosuppressive agents:
 - Concurrent systemic immunosuppressive therapy, in particular systemic corticosteroids, must be stopped 14 days prior to first dose of study treatment. However, subjects are allowed to initiate use of systemic steroids for CNS metastases after the first dose of study treatment.
 - Subjects are allowed to use a physiologic replacement dose of hydrocortisone or its equivalent (defined as up to 30 mg per day of hydrocortisone or up to 10 mg per day of prednisone) or a single dose of systemic corticosteroids.
- Other systemic chemotherapy, immunotherapy, radiotherapy, herbal medications or other treatments intended for antitumor activity. Palliative radiotherapy for peripheral bone metastases is allowed.
- Investigational products or therapy other than ASP1650.

Cautionary Concomitant Treatment

Considerations should be given to avoid or minimize the use of the following concomitant medications, if possible, during ASP1650 treatment:

- Systemic corticosteroids, because their impact on the potential efficacy of ASP1650 is not known.
 - Systemic corticosteroids should be avoided or minimized while subject is on study treatment unless required for management of an emergent medical condition (e.g., severe hypersensitivity reaction).
 - For a subject's first dose of ASP1650, it is recommended that the prophylactic use of corticosteroids be avoided.
 - Inhaled, intranasal and topically applied steroids are allowed.

Prohibited Non-drug Procedures

- Any surgery (including palliative) that involves removal of tumor/metastases masses that may affect the efficacy assessments (removal of small non-measurable masses may be allowed)

A list of excluded medications can be found in [Appendix [12.1](#) List of Excluded Concomitant Medications].

5.1.4 Treatment Compliance

The dose and schedule of ASP1650 administered to each subject will be recorded on the appropriate form at every cycle. Reasons for dose delay, reduction or omission will also be recorded. This information will be used to assess compliance with the treatment.

Compliance with infusion administration and dosing should be monitored closely and any deviations should be reported to the sponsor.

5.1.5 Criteria for Continuation of Treatment

Subjects will be treated with ASP1650 on day 1 of each cycle (each cycle has 14 days). All subjects will be treated for a maximum of 12 cycles or until the subject meets study treatment discontinuation criteria. ASP1650 will not be made available after conclusion of the study to subjects who are still receiving and benefiting from study treatment.

In case of premature study termination, ASP1650 may be made available to subjects who are still receiving study treatment, have not yet completed 12 cycles of treatment and who are still benefiting from study treatment until study defined treatment discontinuation criteria is met.

5.2 Demographics and Baseline Characteristics

5.2.1 Demographics

Demographic information will be collected for all subjects and will include age or date of birth (where permitted), sex, race (where permitted) and ethnicity (where permitted).

5.2.2 Medical History

Medical history includes all significant medical conditions per the judgment of the investigator that have resolved prior to informed consent or are ongoing at the time of consent. Details that will be collected include the onset date and recovery date and NCI-CTCAE grade, if applicable for ongoing conditions.

5.2.3 Diagnosis of the Target Disease, Severity, and Duration of Disease

A complete medical history of the target disease will be recorded at screening. This will include:

- Subject's medical condition
- Date of initial diagnosis
- Tumor location
- Other disease specific information as designated in the eCRF.

5.3 Efficacy and Immunogenicity Assessments

5.3.1 Efficacy Assessments

Disease response and progression will be evaluated in this study using modified RECIST v1.1, incorporating RECIST v1.1 and serum tumor biomarker response criteria. In addition, response assessment using RECIST v1.1 alone for subjects with measurable disease at baseline and serum tumor biomarker response criteria alone for subjects with elevated serum tumor markers ($> 2 \times$ ULN AFP or $> 2 \times$ ULN β hCG) at baseline will be performed as sensitivity analyses.

5.3.1.1 Imaging Assessments

Imaging assessments will be evaluated by the investigator at baseline and every 6 weeks + 7 days counting from C1D1 during the first 24 weeks and then every 12 weeks ± 7 days thereafter until the subject develops radiological disease progression per RECIST v1.1 by local investigator evaluation or starts other systemic anticancer treatment, whichever comes earlier.

All measurable disease must be documented at Screening and re-assessed at each subsequent radiologic evaluation. Imaging will include CT scans with contrast of the thorax, abdomen and pelvis. If the CT scan with contrast is medically not feasible, a CT scan without contrast or MRI may be used for imaging. Bone scans (or focal X-ray) may be performed if metastatic disease in bone is suspected. The same mode of imaging should be utilized throughout the study unless medical necessity requires a change.

Assessment of response using RECIST v1.1 [Eisenhauer et al, 2009] will be based upon local investigator evaluation. Confirmatory scans for CR or PR should be done at least 4 weeks after the date of the scan that CR or PR was first observed.

Response assessments for the primary objective of this trial (ORR) will be made using modified RECIST v1.1. The same measurable and non-measurable lesions determined at baseline will be followed by RECIST v1.1 throughout the study.

5.3.1.2 Response Criteria Based on Modified RECIST v1.1

For subjects with measurable disease at baseline, the following criteria in [Table 4](#) will be used:

Table 4 Response Criteria Based on Modified RECIST v1.1

Serum Markers	Target Lesions	Non-Target Lesions	New Lesions	Overall Timepoint Response Assessment	
	(target lesion response)	(non-target lesion response)	(unequivocal new lesions)		
Values that fall below the ULN for the assay employed	CR	CR	No or Equivocal	CR	
	CR	Not Applicable	No or Equivocal	CR	
	Not applicable	CR	No or Equivocal	CR	
For both AFP and beta-hCG, no increase \geq 50% in 2 samples at least 1 week apart compared to nadir values, at least one of the values are above ULN	CR	CR	No or Equivocal	PR	
	CR	Not Applicable	No or Equivocal	PR	
	Not applicable	CR	No or Equivocal	PR	
For both AFP and beta-hCG, no increase \geq 50% in 2 samples at least 1 week apart compared to nadir values	CR	Non-CR/Non-PD	No or Equivocal	PR	
	CR	NE/ND	No or Equivocal	PR	
	PR	CR	} = not PD	No or Equivocal	PR
	PR	Non-CR/Non-PD		No or Equivocal	PR
	PR	NE/ND		No or Equivocal	PR
	PR	Not applicable		No or Equivocal	PR
For both AFP and beta-hCG, no increase \geq 50% in 2 samples at least 1 week apart compared to nadir values	SD	CR	} = not PD	No or Equivocal	SD
	SD	Non-CR/Non-PD		No or Equivocal	SD
	SD	NE/ND		No or Equivocal	SD
	SD	Not applicable		No or Equivocal	SD
Any	PD	Any	Any	PD	
Any	Any	PD	Any	PD	
Any	Any	Any	Yes or Unequivocal	PD	
Increase \geq 50% in serum tumor markers AFP or beta-hCG in 2 samples at least 1 week apart compared to nadir values	Any	Any	Any	PD	
NE/ND	NE/ND	Not PD	No or Equivocal	NE	

CR: complete response; ND: not done; NE: non-evaluable; PD: progressive disease; PR: partial response; SD: stable disease.

Confirmatory assessment for CR or PR should be done at least 4 weeks after the date of the CR or PR was first observed.

In subjects whose only evidence of disease is elevated serum tumor markers ($> 2 \times$ ULN AFP or $> 2 \times$ ULN β hCG) at baseline, the modified RECIST v1.1 will reduce to serum tumor marker response criteria described in Section 5.3.1.3. In subjects whose only evidence of disease is elevated serum tumor markers ($> 2 \times$ ULN AFP or $> 2 \times$ ULN β hCG) at baseline, confirmatory assessment for CR or PR is not required.

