5.3.1.3 Response Criteria Based on Serum Tumor Biomarkers

Blood will be drawn for the measurement of serum AFP and serum β hCG at day 1 of every cycle and during the post treatment period follow up period to align with imaging assessment (every 6 weeks + 7 days counting from C1D1 for the first 24 weeks and then every 12 weeks ± 7 days thereafter) until the subject develops radiological disease progression per RECIST v1.1 by local investigator evaluation or starts other systemic anticancer treatment. To evaluate the effect of ASP1650 on changes in serum β hCG and AFP, disease response will be derived for subjects with elevated serum tumor markers ($> 2 \times$ ULN AFP or $> 2 \times$ ULN β hCG) at baseline using the following definition:

- CR is defined as values that fall below the ULN for the assay employed. Confirmed CR must remain at that level for at least 4 weeks.
- PR is defined by serum tumor markers (AFP and β hCG) that are decreasing. Elevated serum tumor markers (AFP or β hCG) values must fall $\geq 90\%$ below baseline pretreatment levels for β hCG or 50% decrease below baseline pretreatment levels for AFP. PR must persist for at least 6 weeks to be a confirmed PR. If both tumor markers are elevated and 1 falls below 90%, the other should fall at least below 50% of baseline pretreatment levels.
- Stable disease (SD) is defined as no change or a change in serum tumor biomarkers that does not qualify as CR, PR or PD. Durable SD is defined as SD that is maintained for at least 12 weeks.
- PD is defined as $\geq 50\%$ increase in AFP or β hCG in 2 samples, 1 week apart compared to nadir.

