In subjects whose only evidence of disease is elevated serum tumor markers ($> 2 \times$ ULN AFP or $> 2 \times$ ULN β hCG) at baseline, the modified RECIST v1.1 will reduce to serum tumor marker response criteria. Serum marker criteria can be found in section 5.3.1.3 of the protocol. In subjects whose only evidence of disease is elevated serum tumor markers ($> 2 \times$ ULN AFP or $> 2 \times$ ULN β hCG) at baseline, confirmatory assessment for CR or PR is not required.

Best overall response is determined once all tumor response data for the subject is available. Subjects will be classified by best response on study as outlined in modified RECIST v1.1 criteria. For best overall response of stable disease (SD), SD must be documented as present at least once after study entry and maintained for at least 12 weeks.

ORR as assessed by RECIST 1.1 alone and by serum marker alone will be performed as a sensitivity analysis.

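### Marker progression is a 50% rise over nadir with no level condition, so a rise wholly inside the normal range turns an imaging PR or SD into PD and gives an imaging CR two matching rows

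*Protocol*

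**What the plan says.** Protocol 5.3.1.2, Table 4, defines the overall response at each timepoint for subjects with measurable disease at baseline. SAP 5.1.1, Table 1, repeats it. The marker conditions are:

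- **PD row:** an increase of 50% or more "in serum tumor markers AFP or beta-hCG in 2 samples at least 1 week apart compared to nadir values", with any result allowed in all three imaging columns.
- **PR and SD rows:** "For both AFP and beta-hCG, no increase" of that size over nadir. The first PR block, for a full imaging CR, adds "at least one of the values are above ULN".
- **CR rows:** "Values that fall below the ULN for the assay employed", with nothing about a rise.

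Protocol 5.3.1.3 governs subjects whose only evidence of disease is elevated markers. PD there is again a rise of 50% or more in either marker, "in 2 samples, 1 week apart compared to nadir", and "CR is defined as values that fall below the ULN for the assay employed". The SAP adds nothing of its own: "Serum marker criteria can be found in section 5.3.1.3 of the protocol".

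The protocol does use a level elsewhere. Section 5.3.1 plans "serum tumor biomarker response criteria alone for subjects with elevated serum tumor markers", meaning above 2 x ULN at baseline. That limits who is assessed. It does not set the level at which PD is called.

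**The concern.** Inclusion criterion 11 (Protocol 3.2) asks for measurable disease or a rising marker, so a subject with measurable disease and normal markers is eligible and falls under Table 4. For that subject the PD row reacts to relative fluctuation of a normal value.

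Modified-RECIST PD is the event in PFS and DOR (SAP 5.2.2, 5.2.3). It can interrupt durable SD in CBR (SAP 5.2.1), and it removes the response at each affected timepoint from confirmed ORR. Confirmed ORR drives both Simon decisions (Protocol 7.1, 7.9). Neither document says whether nadir includes baseline, whether the two samples must be consecutive, or which row prevails when two match.

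**Working it through.** **1. Row matching.** Take AFP with nadir 2.0, then 3.2 and 3.1, with beta-hCG flat at 0.5 (ULNs of 10 and 5 assumed for illustration). The ratios are 3.2/2.0 = 1.60 and 3.1/2.0 = 1.55, both at least 1.5 and both far below ULN.

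| Imaging (target / non-target), no new lesion | Row if markers stable | Row(s) with this rise |
|---|---|---|
| PR / CR, non-CR/non-PD, NE/ND or not applicable | PR | PD only |
| SD / the same four | SD | PD only |
| CR / non-CR/non-PD or NE/ND | PR | PD only |
| CR / CR; CR / not applicable; not applicable / CR | CR | CR and PD |

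That is 4 + 4 + 2 + 3 = 13 non-PD imaging combinations. Evaluable markers can be in 5 states: no rise with all values normal; no rise with a value above ULN; a rise wholly below ULN; a rise with some value, but not both samples of the rise, above ULN; and a rise above ULN in both samples. Of 13 x 5 = 65 combinations, 3 match two rows as the table stands.

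**2. Marker-only subjects (Protocol 5.3.1.3).** A rise below ULN during marker CR meets both the CR and the PD definitions. Because PD needs a rise in only one of the two markers, a normal-range rise in a marker that was never elevated is also PD.

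**3. The plan's own design figures.** With X1 ~ Bin(13, p) and X2 ~ Bin(21, p), the trial succeeds if X1 is at least 2 and X1 + X2 is at least 6. The exact type I error at p = 0.10 is 0.0957. Power at p = 0.25 is 0.8108, and the probability of stopping at stage I at p = 0.25 is 0.127. The stated 10% and 80% reproduce.

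**4. Size.** The documents give no marker CV, serial correlation or share of subjects with normal markers, so all three are assumed. The simulation used 200,000 subjects per setting with truly stable markers:

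- lognormal values with log-SD = sqrt(ln(1 + CV²)), a baseline value plus 12 draws at 2-week spacing, and correlation between adjacent draws of 0 or 0.7;
- nadir taken as the running minimum including baseline, and PD as two consecutive values at least 1.5 x nadir;
- scans at weeks 6, 12, 18 and 24, with a response kept if any two adjacent scans are unaffected.

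Observed ORR = 0.25 x (1 - share x loss), entered into the exact Simon calculation. For two normal-range markers:

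| CV | Confirmed response lost (corr 0 / 0.7) | Power, share 20% to 50% (corr 0) | Power, share 20% to 50% (corr 0.7) | False PD by week 12 (corr 0 / 0.7) |
|---|---|---|---|---|
| 10% | 0.0002 / 0.0001 | 0.81 | 0.81 | 0.4% / 0.1% |
| 15% | 0.0192 / 0.0135 | 0.81 to 0.80 | 0.81 | 10% / 4% |
| 20% | 0.1117 / 0.0742 | 0.79 to 0.77 | 0.80 to 0.78 | 33% / 17% |
| 30% | 0.3924 / 0.2710 | 0.75 to 0.62 | 0.77 to 0.69 | 67% / 45% |

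Example at CV 20%, correlation 0, share 50%: 0.25 x (1 - 0.5 x 0.1117) = 0.236, which gives power 0.77. At that CV and correlation, type I error falls to between 0.088 and 0.077. With one normal-range marker, power stays at 0.79 or above up to CV 20%.

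The false-PD column applies within the affected subgroup only. Across all subjects at CV 20%, 33% x (20% to 50%) is about 7% to 16%, and 17% x (20% to 50%) is about 3% to 8%, before true progression competes.

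**The case against.** **The rule may be deliberate.** Inclusion criterion 9 uses the same relative convention, without a level, for marker-only failure of prior therapy. This is a fair point, and it means the entry and response rules must be considered together. It does not resolve the double match, and criterion 9 describes failure of earlier treatment, not loss of an imaging response.

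**PD naturally overrides.** Every PD row accepts any result in the columns it does not test, so override is the likely reading. That stands, and one sentence would settle it. A reader might infer that the primary endpoint is contradictory throughout. It is not: the double match is confined to a full imaging CR and to marker CR.

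**Practice softens it.** Two samples are needed, response is by local investigator evaluation (Protocol 2.2.1), and the RECIST 1.1-alone analyses (SAP 6.4.1.3) would show the loss. All true, but those analyses do not drive the Simon decisions, and investigators without a written rule may code the same data differently.

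**Marker-only PR.** A reader might infer that this rule alone costs a marker-only subject a PR when the never-elevated marker rises. Section 5.3.1.3 does not support that. Its PR definition already asks that AFP and beta-hCG be falling, which arguably blocks PR. Without the PD rule the subject would be SD, unless that clause is limited to markers elevated at baseline.

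**Sample spacing.** Section 5.3.1.3 says 1 week where Table 4 says at least 1 week. Scheduled draws are 14 days apart on treatment and 6, then 12, weeks apart afterwards, so this is a wording difference to align and not a separate defect.

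**Conclusion.** The gap is in the text and needs no assumption: a rise wholly inside the normal range is progression under Table 4 and under 5.3.1.3, and the CR definitions overlap with it. It should be fixed.

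The consequence for ORR is conservative. A reader might infer that the Simon design is invalid or seriously underpowered. The figures do not support that: type I error is not inflated, and the power loss is negligible at CV 10%, small up to CV 20% (0.81 to 0.77) and large only at CV 30% (0.77 to 0.62). The effect on PFS within the affected subgroup is larger, at 17% to 33% false PD by week 12 at CV 20%, but PFS is a descriptive Kaplan-Meier summary with no test.

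These sizes rest on the assumed CV, correlation and share, on every normal-range value being quantifiable, and on best response counting any unaffected pair of scans. The loss would be greater if responses after PD were not counted, which the documents do not state.

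**What to change.** For endpoint derivation only, in SAP 5.1.1:

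1. Define marker PD once: AFP or beta-hCG at least 50% above nadir and above the assay ULN in both of two samples at least 1 week apart. Use it in the PD row of Table 1 and for marker-only subjects.
2. Use marker PD not met as a condition in the CR, PR and SD rows, keeping "at least one of the values are above ULN" in the first PR block. Changing the PD row alone would leave 23 of the 65 combinations with no row (10 for a rise wholly below ULN, 13 for a rise only partly above it). With the full edit, all 65 match exactly one.
3. State that PD takes precedence if two rows match.
4. State whether nadir includes baseline, whether the samples must be consecutive, whether a response after PD counts in best overall response, and whether the falling-marker clause in Protocol 5.3.1.3 applies only to markers elevated at baseline.
5. State how markers that are not evaluable or not done combine with imaging CR, PR or SD. The 65-combination check does not cover these.

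The study is open-label and, by Protocol 1.3, already dosing in June 2019. Relaxing PD could turn known non-responders into responders. Record the date and reason for the change, and also report ORR, CBR, DOR and PFS under the current table.

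**Cost.** No new data or visits, but Protocol Table 4 needs an amendment. Some true early rises would be dated later, at ULN crossing. Markers near ULN stay partly exposed: at 0.8 x ULN with two markers, residual false PD by week 12 is about 7% to 8% at CV 20%; at 0.5 x ULN it is 0.1% or less with independent draws and at most 1.2% (CV 30%, correlation 0.7).

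The sponsor should reconcile inclusion criterion 9, Protocol Table 4, Protocol 5.3.1.3, the marker-progression criterion in Protocol 6.1 and SAP Table 1 with each other. No rule for stopping treatment is proposed, and Protocol 6.1 is not made subordinate to the derivation definition.
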